2.2 Secondary estimands

Not applicable

3 Study design

Figure 3-1 Study Design

This is a non-confirmatory, randomized, double-blind, placebo-controlled, parallel-group trial in participants with TRD to evaluate the efficacy, safety, tolerability and pharmacokinetics of single subcutaneous MIJ821 administration in addition to pharmacological antidepressant SoC treatment. Approximately 56 participants will be randomized in a total of 20-25 centers worldwide.

Participants will be randomly allocated to one of the following four treatment arms in a 1:1:1:1 ratio:

- Single administration of MIJ821 s.c. 10 mg
- Single administration of MIJ821 s.c. 4 mg
- Single administration of MIJ821 s.c. 1 mg
- Single administration of Placebo s.c.

The screening period starts when the participant signs the informed consent form and can last up to 28 days. The eligibility of participants is determined based on the assessments performed during the screening period and also on Day 1, prior to randomization. With the exception of lab results, all other baseline evaluations including the primary efficacy scale (MADRS) must be performed on Day 1, prior to randomization, and reviewed against the eligibility criteria before dosing. On Day 1, eligible participants will then be randomized to one of the above treatment arms.

Treatment is administered as a single s.c. injection on Day 1, followed by a safety observation at the clinical site for a minimum of 4 hours after administration. Study participants will be continuously observed by site personnel during the first 30 minutes after administration for emergence of adverse events, particularly CNS or cardiovascular AEs. Safety assessments will

include physical examinations (PEs), ECGs, vital signs, standard clinical laboratory evaluations (hematology, blood chemistry, and urinalysis), administration of the CADSS, MOAA/S, C-SSRS, and memory assessment using orientation questions. Local tolerability will be evaluated by visual inspection of the injection area. Injection site abnormalities reaching the threshold of mild changes will also be assessed quantitatively (refer to Section 8.5.4).

Participants will be allowed to leave the clinical site at the earliest 4 hours after dosing, if all of the following criteria are fulfilled:

- The participant does neither report nor present with any CNS adverse events (dissociation, amnesia, sedation)

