- There is no increase in suicidal intensity or new occurrence of suicidal ideation as assessed by C-SSRS
- No clinically relevant QTcF prolongation (QTcF≥500 msec or increase in QTcF from baseline≥60 msec)
- No clinically relevant abnormalities in blood pressure (BP) (90≤Sysotlic BP (SBP) ≥180 mmHg or 50≤Diastolic BP (DBP) ≥105 mmHg or increase or decrease in SBP of at least 20 mmHg or increase or decrease in DBP of at least 15 mmHg from baseline) or any increase in BP that is accompanied by symptoms, such as headache, dizziness, nausea, visual disturbances or other neurological symptoms
- The investigator does not identify any other AEs that require continued monitoring

If the participant cannot be released from the clinical site 4 hours after dosing, extended safety monitoring will be performed as described below.

The post-dose follow-up period will continue for 4 weeks (28 days) after treatment. On-site visits to assess efficacy and safety are scheduled on Day 2 (24 hours post-dose) and subsequently every week (i.e., on Days 8, 15, 22 and 29) during the follow-up period. The assessment to address the primary objective will be performed at Day 2 (24 hours post-dose). Phone calls will be conducted 3 days after each on-site visit with the exception of End-of-study (EOS) visit. The EOS visit will be completed on site on Day 29. The total duration of the study is approximately 8 weeks (56 days), including screening.

Extended safety monitoring in case of AEs on Day 1 (4 hours after dosing)

If extended monitoring is required beyond the minimum 4 hours of monitoring on Day 1, the following will be assessed:

- Monitoring of CNS adverse events (dissociation, amnesia, sedation):
 - If there are any dissociative AEs, amnesia or somnolence/sedation present, the participant should be monitored at the clinical site until these AEs are fully resolved. If the dissociative AEs or cognitive symptoms do not resolve within 6 hours after onset, the participant will be required to stay at the clinical site for overnight monitoring and can be discharged after the assessments are completed on Day 2 and the AEs have resolved. The onset and resolution time of dissociative and cognitive AEs should be captured as accurately as possible. The following assessments are recommended to follow CNS AEs, whenever possible (e.g., participant is awake):

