- Dissociative AEs were among the most common AEs in the study. They were dose dependent, but not observed at 0.16 mg/kg i.v. dose or lower. The range for time to onset from start of infusion was 0.78-3.43 hours and the time to resolution from onset was 1.15-5.35 hours after a single dose of MIJ821.
- Amnesia was also among the most common AEs in the study. It was observed at 0.32 and 0.48 mg/kg i.v. dose. The range for time to onset was 0.83-7.83 hours after start of infusion and the time to resolution from onset 0.02-23.85 hours after a single dose of MIJ821.

Monitoring and mitigation in the current study

- Monitoring at the clinical site for minimum 4 hours on the day of MIJ821 administration and longer, if any dissociative or amnestic AEs are observed
- Routine AE collection and routine memory assessment questions
- Routine AE collection and regular administration of the CADSS
- Participants with current diagnosis and history of neurological or psychiatric disorders (including drug and alcohol abuse) other then TRD will be excluded

- J-ESS study relevant results
- No dissociative AEs or amnesia were reported in the study at any dose of i.v. MIJ821 (0.016-0.16 mg/kg).
- SAD study with s.c. MIJ821 (study ongoing, preliminary results from the first cohorts see Section 1.1.3 for details)
- Preliminary, blinded data with s.c. MIJ821 are available from the ongoing double blind, placebo controlled SAD study (MIJ821A02201). In this study, Dissociative AEs were reported in the 4 and 12 mg cohorts, where MIJ821 exposure was comparable to that reached by 0.048 and 0.16 mg/kg i.v. doses in the FIH study, respectively. All of these events were mild or moderate in severity and resolved without treatment.
- PoC study relevant results
- Dissociative AEs were among the most common AEs in the study and were observed at both doses used in the study (0.16 and 0.32 mg/kg, i.v.). The time to onset was quick (up to 0.7 hour after start of infusion), and the time to resolution ranged from 1.6 to 7.0 hours after onset.
- Amnesia was also among the most common AEs in the study, it
 was also observed at both 0.16 and 0.32 mg/kg i.v. doses with higher
 incidence at the higher dose. The time to onset was also quick (up to
 0.7 hour after start of infusion), and the time to resolution ranged from
 0.7 to 9.2 hours after onset.

CNS / Suicidality

- FIH and J-ESS study relevant results
- No relevant findings were identified based on AEs and the C-SSRS scale.

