10.2.5 Adverse events of special interest

Based on the current available information, considering the ketamine safety profile and clinical/non-clinical evidence available for MIJ821, following events are considered AESI. This information is subject to change, based on the availability of incremental clinical experience with MIJ821. Please refer to the current Investigator Brochure for the most updated information on safety profile.

- Dissociation
- Sedation
- Cardiovascular effects (BP changes and QT interval prolongation on ECG)
- Respiratory effects (difficulty in breathing, changes in oxygen saturation)
- Suicidality (suicidal ideation or behavior)
- Memory gaps/ amnesia
- Cystitis or lower urinary tract adverse events

The list of current adverse events of special interest is available in the IB.

Post dose observation / Hospitalization

A four-hour post-dose observation period is implemented in this trial to ensure patients' safety and give required time for the potential events of interest to onset. Most of the events of interest should also be resolved by the end of the suggested observation period. The adverse events of interest should be followed up on site until resolution or until absence of safety risk assessed by the investigator based on clinical evaluation and judgement. If severe dissociative, psychotic, suicidal, sedative, cardiovascular or agitated symptoms emerge, it is recommended investigators hospitalize participants until those adverse events are resolved. If they persist, or based on clinical judgment or patient preference, those participants can be discontinued from the study at any time.

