In case of a safety concern or worsening of depressive symptoms including suicidal ideation, participants' hospitalization should be prolonged or they can be re-hospitalized at any timepoint of the study overnight or for a longer period until they improve clinically, as per investigator clinical judgement. If suicidal symptoms are present to a moderate to severe degree, either based on rating scales or investigator judgment, and such symptoms persist throughout the above mentioned monitoring period following the intravenous infusion, investigators must hospitalize participants at least overnight. If suicidal symptoms are mild, either based on rating scales or investigator judgment, the investigator's judgment can be used to allow the participant to leave the clinical setting, but in that case arrangements should be made such that family members or friends are present with the participant for at least 24 hours. If such arrangements cannot be made, it is recommended that the participant is hospitalized at least overnight.

Caution with performance of potentially dangerous tasks

Given that MIJ821 may impair the mental or physical abilities required for the performance of potentially dangerous tasks such as driving a car or operating machinery, participants should be advised about these potential risks. If the participant is feeling drunk or dizzy or if he/she experiences visual disturbances, hallucinations, or euphoric mood, then he/she should not drive, use machines or perform any other tasks that require his/her attention and good coordination.

In case of a safety concern, the participant should be hospitalized (or hospitalization should be prolonged) as per investigator's judgement until resolution of these events or absence of a safety risk.

Scales / tools to assess CNS related AEs

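### Section 10.2.5 lets on-site follow-up of dosing-day dissociation, amnesia and sedation end earlier than Section 3 allows, and no text says which rule prevails

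*Protocol*

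**What the plan says.** Section 3 (Study design) sets the conditions for leaving the site, at the earliest 4 hours after dosing. All of them must be met, and the first is: "The participant does neither report nor present with any CNS adverse events (dissociation, amnesia, sedation"). It carries no severity threshold and no exception for investigator judgement. If such an event is present, "the participant should be monitored at the clinical site until these AEs are fully resolved". A further step follows: "If the dissociative AEs or cognitive symptoms do not resolve within 6 hours after onset, the participant will be required to stay" at the site overnight, and such a participant "can be discharged after the assessments are completed on Day 2 and the AEs have resolved". Table 4-1 in Section 4.5 agrees in direction: on-site monitoring lasts at least 4 hours "and longer, if any dissociative or amnestic AEs are observed".

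Section 10.2.5 lists dissociation, sedation and memory gaps/amnesia among the events of special interest. Its paragraph on post-dose observation and hospitalization opens with the same four-hour period. It then says that all those listed "should be followed up on site until resolution or until absence of safety risk assessed by the investigator based on clinical evaluation and judgement". On hospitalization it says: "If severe dissociative, psychotic, suicidal, sedative, cardiovascular or agitated symptoms emerge, it is recommended investigators hospitalize participants until those adverse events are resolved".

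**The concern.** Both texts cover the same three events in the same post-dose period, but they end on-site follow-up at different points. Section 3 accepts resolution only. Section 10.2.5 accepts resolution or an investigator's judgement that no safety risk remains. Section 10 is where site staff would look for the handling of events of special interest, and a reader who stops there would not learn of the 6-hour overnight rule for CNS events. What is at stake is the safety of a participant sent home with residual dissociation, amnesia or sedation, and uniform discharge practice across 20-25 centers. Whether such a release counts as a protocol deviation would also be open to dispute.

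**Working it through.** The plan states no figure to reproduce, so the check sets the two rules side by side and then asks whether the case in which they differ can occur.

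| Question | Section 3 | Section 10.2.5 |
|---|---|---|
| Events | Dissociation, amnesia, sedation | The same three, among seven groups |
| Severity | Any | Any for follow-up; severe for hospitalization |
| End of on-site follow-up | Full resolution | Resolution, or no safety risk in the investigator's judgement |
| Overnight trigger for CNS events | More than 6 h after onset (dissociative or cognitive) | None |
| Pointer to the other section | None on this point | None; it points to Sections 6.2.3, 9.1.1, 10.2.3, 10.2.4 and 16.1 and to the Investigator's Brochure |

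The 6-hour clock runs from onset of the event, not from dosing. The sentence with that clock does not name sedation, but Section 10.1.1 gives amnesia and sedation as examples of cognitive events.

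**Is the looser end point confined to other events or later visits?** No. The paragraph begins with the four-hour observation on the dosing day, and the three CNS events are on its list.

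**Does Section 10.2.5 repeat Section 3's overnight rules?** It does so for moderate to severe suicidal symptoms: if "such symptoms persist throughout the above mentioned monitoring period following the intravenous infusion, investigators must hospitalize participants at least overnight". It has no counterpart for CNS events. (The reference to an infusion in this s.c. trial is a separate wording slip and plays no part in this point.)

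**Can the two rules give different answers in practice?** Inputs are from Table 4-1, proof-of-concept study (i.v.): onset up to 0.7 h after start of infusion; longest time from onset to resolution 7.0 h for dissociation and 9.2 h for amnesia. The lower onset bound of 0 h is my assumption.

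- Excess over the 6 h rule = longest duration − 6. Dissociation: 7.0 − 6 = 1.0 h. Amnesia: 9.2 − 6 = 3.2 h.
- End of event = onset + duration. Dissociation: 0 + 7.0 = 7.0 h to 0.7 + 7.0 = 7.7 h. Amnesia: 0 + 9.2 = 9.2 h to 0.7 + 9.2 = 9.9 h.
- Excess over the 4 h minimum stay = end − 4. Dissociation: 3.0 to 3.7 h. Amnesia: 5.2 to 5.9 h.

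So events of these lengths would still be present at 4 h and would pass the 6 h trigger. If they were mild and judged to carry no safety risk, Section 10.2.5 would let on-site follow-up end, while Section 3 would require an overnight stay.

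**Severity.** Section 1.1.3 reports that all dissociative events so far with s.c. dosing were mild or moderate (preliminary blinded data in healthy volunteers). Section 10.2.5 recommends no hospitalization for those grades.

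**The case against.** The strongest reply is that the rules are cumulative. Section 3 is a gate, Section 10.2.5 never says that a participant with a CNS event may leave, and a site that released one would breach Section 3. The general paragraph in Section 10.2.5 also covers respiratory and urinary events, which have no Section 3 rule of their own, so a judgement standard is natural there. Section 3 itself leaves other AEs needing continued monitoring to the investigator. And hospitalization for severe symptoms can be read as an addition to on-site monitoring, not a substitute for it.

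Much of this stands, and it is why the point is minor. It does not remove the conflict. For these three events Section 10.2.5 states a second end point that Section 3 excludes, and no text tells the site to disregard it. Section 3's judgement clause concerns AEs other than those it has already listed, so it does not soften the CNS criterion.

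A reader might go further and treat the similar wording under Sedation in Section 4.5, and in the Section 10.2.5 caution on dangerous tasks, as more instances of the same fault. The documents do not support that. Those sentences follow the advice on driving and machinery and concern how long a hospitalization for a safety concern lasts, not dosing-day release. Nor is a defect shown for QTcF, blood pressure or suicidality: Section 3's own blood pressure and mild-ideation rules already allow investigator judgement.

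**Conclusion.** Section 10.2.5 is wrong as written for dissociation, amnesia and sedation on the dosing day. The inconsistency is minor. It affects participant safety and consistency of discharge between sites, and it does not touch the primary analysis.

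The wording difference is certain; that a site would act on the looser text is a possibility, not a prediction. The durations show only that events long enough to matter have occurred. They are maxima after i.v. dosing, reported across 0.16 and 0.32 mg/kg, whereas 10 mg s.c. was chosen to match 0.16 mg/kg, with a simulated mean Cmax 18% lower. In the first-in-human study the longest dissociation was 5.35 h, under the trigger. Amnesia there lasted up to 23.85 h, but was observed only at 0.32 and 0.48 mg/kg. No duration is given for s.c. events.

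A reader might infer that a sizeable number of participants would be sent home early. The documents do not support any such number, because the share of events lasting beyond 4 or 6 hours is not given. Nor do they support saying that the protocol lacks an overnight rule for CNS events: Section 3 has one, and it is clear.

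**What to change.** In Section 10.2.5, in the paragraph on post-dose observation and hospitalization, add: *For dissociation, amnesia and sedation on the dosing day, the Section 3 release and overnight-stay criteria apply; the absence-of-safety-risk end point does not apply to these events.* This supplies both the precedence and the missing pointer. The end point for the other events of special interest can stay as it is, and no change is needed in Section 4.5 or in the caution on dangerous tasks.

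The cost is one sentence at the next amendment, with no change to visits, scales or analysis. The only downside is that a participant who would have been released under Section 10.2.5 stays longer, which Section 3 already requires.

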2.1 Primary estimands

The primary clinical question of interest is: What is the effect of s.c. MIJ821 (versus placebo) given in addition to standard pharmacological antidepressant (SoC) treatment 24 hours after the injection of the study drug on change in depressive symptoms in participants with TRD, who have already failed to adequately respond to at least two conventional antidepressants.

Rationale

The justification for the primary estimand is that it will allow to estimate the rapid effect of the study drug in a population of depressed participants, who are considered treatment resistant, based on the definition above. A rapid response is clinically valuable as conventional antidepressants might need several weeks to achieve reduction of depressive symptoms.

The primary estimand is described by the following attributes:

- 1. Population: participants with treatment resistant depression, who have failed to show adequate treatment response to at least 2 antidepressants previously.
- 2. Primary variable: change from baseline to 24 hours post dose in the MADRS total score.
- 3. Treatment of interest: the randomized treatment (the investigational treatment MIJ821 or the placebo treatment) administered as a single s.c. injection on Day 1. The dose of the allowed concomitant medication (i.e., SoC) for depression must remain stable during the trial.
- 4. Handling of intercurrent events (IEs) prior to MADRS assessment at 24 hours (for more details see Section 12.4.3):
 - New intake or change in concomitant medications/therapies which have a potential confounding effect: hypothetical strategy
 - Intake of prohibited medications: hypothetical strategy
 - Intake of rescue medications: hypothetical strategy
 - IEs related to pandemic: hypothetical strategy
 - IEs leading to study discontinuation due to adverse (AEs), lack of efficacy or other reasons: treatment policy

Participants who took prohibited medications, rescue medications, or took new or change concomitant therapy which have potential confounding effect, will continue in the study and be assessed as scheduled.

Further details about the concomitant therapy, prohibited and rescue medications are provided in Section 6.2.

The summary measure: difference in variable means between study drug and placebo.

[figure not shown]
The Multiple Comparisons Procedures - Modeling (MCP-Mod) approach will be used to assess the primary objective (for more details on this approach see Section 12.4.2).

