6.2.4 Restriction for study participants

For the duration of the study, participants should be informed and reminded of the restrictions outlined in this section.

^{**} Participants who are in the post dose follow-up period should continue the follow-up even if they are taking prohibited medications.

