Guidance issued by local regulatory bodies on this aspect prevail and must be implemented and appropriately documented (e.g. the presence of an impartial witness, sign/dating separate ICFs by trial participant and person obtaining informed consent, etc.).

8 Visit schedule and assessments

The Assessment Schedule (Table 8-1) lists all study assessments and when they are performed. All data obtained from these assessments must be supported in the participant's source documentation.

Participants should attend on-site study visits as outlined in the assessment schedule (Table 8-1) or as close to the designated day/time as possible. This is especially important for the Day 2 visit at which primary efficacy assessments are performed. Missed or rescheduled visits should not lead to automatic discontinuation. In addition, the participant will be contacted by phone in between on-site visits (Follow-up call) to collect information about adverse events and concomitant medications. In case follow-up calls have to be shifted by +/- 3 days, follow-up calls can be replaced by on-site visits in accordance to the original visit schedule.

In case a visit is performed outside the schedule, subsequent visits shall be performed in accordance to the original visit schedule. In addition to the scheduled visits, participants may have unscheduled visits for safety monitoring purposes at the discretion of the Investigator. Data collected during unscheduled visits will be recorded in the unscheduled visit CRFs.

Participants who discontinue from the study or withdraw their consent/oppose the use of their data/biological samples should be scheduled for a final evaluation visit if they agree, as soon as possible, at which time all of the assessments listed for the final visit will be performed. At this final visit, the adverse events and concomitant medications not previously reported must be recorded on the CRF.

The "X" in the table denotes the assessments to be recorded in the clinical database or received electronically from a vendor. The "S" in the table denotes the assessments that are only in the participant's source documentation and do not need to be recorded in the clinical database.

Every effort will be made to draw the PK samples at the protocol specified timepoints. Other assessments (e.g., ECG, vital signs, etc.) will be taken prior to the PK sample.

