9.1 Discontinuation from study treatment and from study

9.1.1 **Discontinuation from study treatment**

This is a single dose study, therefore treatment discontinuation for the individual participant is not applicable.

9.1.2 **Discontinuation from study**

Discontinuation from study is when the participant permanently stops further protocol-required assessments or follow-up.

If the participant agrees, a final evaluation at the time of the participant's study discontinuation should be made as detailed in the assessment table (refer to Section 8).

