### 1.2.1 Primary estimand(s)

The primary clinical question of interest is: What is the effect of s.c. MIJ821 (versus placebo) given in addition to standard pharmacological antidepressant (SoC) treatment 24 hours after the injection of the study drug on change in depressive symptoms in participants with TRD, who have already failed to adequately respond to at least two conventional antidepressants.

The justification for the primary estimand is that it will allow to estimate the rapid effect of the study drug in a population of depressed participants, who are considered treatment resistant, based on the definition above. A rapid response is clinically valuable as conventional antidepressants might need several weeks to achieve reduction of depressive symptoms.

The primary estimand is described by the following attributes:

1. Population: participants with treatment-resistant depression, who have failed to show adequate treatment response to at least 2 antidepressants previously.
2. Primary variable/endpoint: change from baseline in MADRS total score at 24 hours post-dose.
3. Treatment of interest: the randomized treatment (the investigational treatment MIJ821 or the placebo treatment) administered as a single s.c. injection on Day 1. The dose of the allowed concomitant medication (i.e., SoC) for depression must remain stable during the trial.
4. Handling of intercurrent events (IEs) prior to MADRS assessment at 24 hours:
  - New intake or change in concomitant medications/therapies which have a potential confounding effect: hypothetical strategy
  - Intake of prohibited medications: hypothetical strategy
  - Intake of rescue medications: hypothetical strategy
  - IEs related to pandemic: hypothetical strategy
  - IEs leading to study discontinuation due to adverse events (AEs), lack of efficacy or other reasons: treatment policy

The summary measure: difference in variable means between study drug and placebo.

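### Treatment policy for study discontinuation before 24 hours needs a 24-hour MADRS, but the visible text offers only an optional final evaluation that may not supply a valid one

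*Protocol*

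**What the plan says.** - **Only one kind of discontinuation exists.** Protocol 9.1.1: "This is a single dose study, therefore treatment discontinuation for the individual participant is not applicable". Protocol 9.1.2: "Discontinuation from study is when the participant permanently stops further protocol-required assessments or follow-up".
- **It is allowed after dosing.** Protocol 10.2.5 recommends hospitalisation for severe dissociative, psychotic, suicidal, sedative, cardiovascular or agitated symptoms until they resolve, and adds: "If they persist, or based on clinical judgment or patient preference, those participants can be discontinued from the study at any time".
- **The estimand.** Protocol 2.1: "IEs leading to study discontinuation due to adverse (AEs), lack of efficacy or other reasons: treatment policy". SAP 1.2.1 says the same. Protocol 12.4.1 and SAP 2.5.1 limit this to discontinuation before the 24-hour assessment.
- **What is offered on leaving.** Protocol 9.1.2: "If the participant agrees, a final evaluation at the time of the participant's study discontinuation should be made as detailed in the assessment table". Protocol Section 8 asks for this visit "as soon as possible, at which time all of the assessments listed for the final visit will be performed". Table 8-1 marks MADRS at the final (Day 29) visit.
- **Medication events are treated differently.** Protocol 2.1 and 12.4.1 keep these participants in the study with their scheduled assessments. The footnote to Table 6-2 adds: "Participants who are in the post dose follow-up period should continue the follow-up even if they are taking prohibited medications".
- **Window and recall.** SAP Table 2-1 maps only study day 2 to the 24-hour visit. SAP 2.5.1.1 gives the since-last-evaluation recall to the 24-hour MADRS alone. The 4-hour MADRS has its own 4-hour form, and every other MADRS uses 7 days.

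**The concern.** Treatment policy takes the outcome as it is, whether or not the intercurrent event occurred. It can be estimated from observed data only if the outcome is still measured after the event. Here the event is itself defined as the end of measurement, and with a single injection already given, leaving the study changes nothing except data collection.

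The collection rules also run opposite to what the strategies need. Medication events have a hypothetical strategy, under which the score after the event is not the target, yet their assessments are expressly kept. Discontinuation has the strategy that does need the later score, and no visible text asks for it.

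At stake is the primary variable in the participants who tolerate the drug worst. Protocol 4.2.1 reports that dissociation became more frequent with dose in the subcutaneous healthy-volunteer study, so lost scores would probably be related to dose, which is the axis that MCP-Mod tests and models.

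**Working it through.** **1. Can the final evaluation stand in for the 24-hour MADRS?** Take a participant who discontinues before the Day 2 visit.

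| When the final evaluation takes place | Analysis visit (SAP Table 2-1) | Recall for a final-visit MADRS (SAP 2.5.1.1) | Valid 24-hour score? |
|---|---|---|---|
| Declined | none | none | No |
| Day 1 | Day 1 | 7 days | No, outside the window |
| Day 2 | 24 hours | 7 days | In the window, wrong recall |
| Day 3 to 11 | Day 8 | 7 days | No, outside the window |

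On Day 2 about 1 of the 7 recalled days is post-dose, so 7 − 1 = 6 days, or 6/7 = 86%, are pre-dose. That score would fall in the 24-hour window while rating mostly the period before treatment. No row yields the primary variable as SAP 2.5.1.1 defines it, unless the site uses the Day 2 form, which no visible text tells it to do.

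**2. Do other rules secure the score?** Protocol Section 3 keeps a participant on site overnight, with discharge after the Day 2 assessments, if dissociative or cognitive events last more than 6 hours. Section 3 and 10.2.5 also require at least an overnight stay for moderate to severe suicidality. The first rule ties discharge to the Day 2 assessments; the suicidality rule does not. Neither covers the cardiovascular, psychotic or agitated symptoms also named in 10.2.5, and neither limits its permission to discontinue at any time.

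**3. The plan's own figure.** Protocol 12.8.1 and SAP Section 3 state about 90% power with 14 per arm and one-sided alpha 0.05. This cannot be reproduced, because the effect size, SD and candidate curves are not in the public text. As a plausibility check, a simulation of the MCP-Mod maximum contrast test (200,000 draws) used six assumed sigmoid Emax curves (ED50/Hill 0.5/1, 1/1, 2/1, 4/1, 2/3, 4/4). Maximum effects of 1.0 and 1.05 SD gave mean power of 88% and 91%, so the stated figure is plausible but not confirmed.

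**4. Cost in precision if scores are lost.** The losses below are assumptions; the documents give none.

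| Scores lost (1 / 4 / 10 mg) | Mean power at 1.0 SD | Mean power at 1.05 SD |
|---|---|---|
| 0 / 0 / 0 | 88.4% | 91.0% |
| 0 / 0 / 1 | 87.6% | 90.2% |
| 0 / 1 / 2 | 86.5% | 89.1% |
| 1 / 2 / 4 | 83.8% | 86.7% |

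The fall is 0.8 points in the mildest case and 4.3 to 4.6 points in the worst. For one dose against placebo with m of 14 scores lost, the SE ratio is √[(1/14 + 1/(14 − m)) / (2/14)], which is 1.019, 1.041 and 1.066 for m = 1, 2 and 3, an increase of 2% to 7%.

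**The case against.** **Such exits should be rare.** The permission in 10.2.5 is optional and follows a recommendation to hospitalise. It runs over the whole follow-up, while only exits before 24 hours touch the primary variable. In the proof-of-concept study dissociation resolved in 1.6 to 7.0 hours and amnesia in 0.7 to 9.2 hours (Table 4-1). Dissociative events in the subcutaneous study were all mild or moderate (Protocol 1.1.3), whereas 10.2.5 concerns severe symptoms. The overnight rules keep many affected participants on site. All of this stands and limits the size of the problem. It also shows that the score could often be obtained.

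**A reader might infer that 9.1.2 ends every assessment and that the 24-hour MADRS is never collected.** The documents do not support that. The same section offers a final evaluation, the final visit includes MADRS, and the Section 3 overnight pathway completes the Day 2 assessments.

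**A reader might also infer a bias of known size in the dose means**, by treating the lost scores as missing at random. That does not follow either. Protocol 12.4.4 and SAP 2.5.4 confine that assumption to missing values unrelated to intercurrent events, and discontinuation is an intercurrent event. The handling of these cases (Protocol Table 12-1 and the matching SAP text) is not public, and the SAP abbreviation list includes missing not at random, so another approach may be specified. Nothing in the documents says how many would leave or how their scores would differ.

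**Nor does the plan clearly cut off safety follow-up.** Protocol 10.1.1 requires adverse events to be followed until they resolve or are judged permanent. How that fits with discontinuing a participant whose symptoms persist needs reconciling, but it is a safeguard.

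**Conclusion.** The point holds as a gap between estimand and data collection. Discontinuation before 24 hours is assigned treatment policy, and no visible text secures a valid 24-hour MADRS after it; the optional final evaluation, taken as written, misses either the window or the recall.

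The likely size is small. Under the assumed curves and losses, power falls by roughly 1 to 5 points. The more important consequence is that the missing scores would probably be related to dose, so the affected arm means would rest on imputation where an observed score was within reach. With 14 per arm, each lost score is 1/14 = 7% of an arm. No bias figure can be attributed to the plan. The conclusion assumes that the non-public text contains no rule requiring the Day 2 MADRS after discontinuation. If it does, only the mismatch with 9.1.2 and Section 8 remains.

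**What to change.** 1. **Protocol 9.1.2 and Section 8.** Add that a participant who discontinues before the Day 2 visit is asked, if they agree, to complete the MADRS at 24 hours post-dose with the since-last-evaluation recall, and that this score enters the primary analysis under treatment policy. Withdrawal of consent (9.2) stays outside this rule. SAP 2.4.1 removes MADRS scores collected after unblinding, so the addition should say whether that still applies to participants whose code was broken.
2. **Reconcile passages.** Protocol 10.2.5 should be brought into line with 2.1 (treatment policy), Section 3 (overnight stay and Day 2 assessments), 9.1.2 (definition of discontinuation) and 10.1.1 (follow-up of adverse events). Which clinical rule governs leaving the study is for the sponsor and investigators to settle.

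The cost is a sentence or two in a protocol amendment. The visit, scale and raters already exist. The downside is that unwell participants are asked for one assessment, which they may decline.
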